### 9.3.4. Management of Pericardial toxicity

Subjects will be assessed for evidence of pericardial events during scheduled visits according to the schedule in Table 10-1. The following findings would heighten suspicion of pericardial effusion or pericarditis and prompt immediate evaluation by ECHO:

Symptoms: shortness of breath, orthopnea, chest pain, dizziness, rapid pulse

- Clinical exam: hypotension, jugular venous distension, pulsus paradoxus, faint heart sounds, friction rub, and/or arrhythmia
- ECG: sinus tachycardia, atrial fibrillation, atrial flutter, low voltage with non specific ST-T wave changes and ST elevation or PR depressions, arrhythmia
- Chest X-ray: widening cardiac silhouette

ECHOs will categorize pericardial fluid as minimal (or trivial), small, moderate or large and will assess for hemodynamic compromise.

Pericardial effusions will be assessed as follows (Table 9-4):

• Minimal (or trivial): A small echo-free space in the posterior atrioventricular groove that is visible only in systole when the heart has pulled away from the pericardium. Typically represents a normal amount of pericardial fluid in a disease-free state.

- Small: <1 cm of posterior echo-free space, with or without fluid accumulation elsewhere, present throughout the cardiac cycle, including diastole (and not only systole).
- Moderate: 1 to 2 cm of echo-free space. Moderate effusions tend to be seen along the length of the posterior wall but not anteriorly.
- Large: >2 cm of maximal separation. Large effusions tend to be seen circumferentially.
- Hemodynamic compromise: RV compression, IVC dilation without respiratory variation, abnormal flow variation across the AV valves without respiratory variation, enlarged or collapsed ventricles. RA diastolic collapse in isolation is too non-specific to signal hemodynamic compromise, but should be considered consistent with this diagnosis when accompanied by other findings

Category	Definitions	Subject Management	
Minimal (or trivial)	A small echo-free space in the posterior atrioventricular groove that is visible only in systole when the heart has pulled away from the pericardium. Typically represents a normal amount of pericardial fluid in a disease-free state.	Increased ECHO and ECG monitoring  : -Weekly until the minimal (or trivial) effusion is no longer present or has not progressed (to a small or greater effusion) over a period of 2 weeks to validate the findings as non- pathologic or until the effusion has regressed (if sooner); - Regular schedule afterwards (i.e., prior to each subsequent cycle).	
Small	<1 cm of posterior echo-free space, with or without fluid accumulation elsewhere, present throughout the cardiac cycle, including diastole (and not only systole).	Increased ECHO and ECG monitoring: -Weekly for the first month after the new pericardial effusions are first noted or until the effusion has regressed (if sooner). - Treatment for the effusion may be administered at the discretion of the Investigator. - Study drug will not be discontinued in these subjects, at the discretion of the investigator, unless the effusion progresses.	
Moderate	1 to 2 cm of echo-free space. Moderate effusions tend to be seen along the length of the posterior wall but not anteriorly.	Remove from study treatment; refer to _cardiologist for follow up as clinically indicated,	
Large	>2 cm of maximal separation. Large effusions tend to be seen circumferentially.	until resolution or stabilization.	
Hemodynamic Compromise	RV compression, IVC dilation without respiratory variation, abnormal flow variation across the AV valves without respiratory variation, enlarged or collapsed ventricles. RA diastolic collapse in isolation is too non-specific to signal hemodynamic compromise, but should be considered consistent with this diagnosis when accompanied by other findings	Remove from study treatment; refer to cardiologist for follow up as clinically indicated, until resolution or stabilization.	

#### Table 9-4. Pericardial Effusion Echocardiographic Assessment and Subject Management Guidelines

 Subjects with ECHO findings of minimal (or trivial) effusion may be discontinued from the study at any time if judged in the subject's best interest, following discussion between the Investigator and the Medical Monitor.

Subjects who are found to have moderate or large pericardial effusions (as defined above) and/or evidence of hemodynamic compromise (regardless of the size of the pericardial effusion) will be immediately removed from study treatment and will be managed according to the accepted standard of care at the discretion of the Investigator. Subjects should be referred to cardiologist for follow up as clinically indicated, until resolution or stabilization.

Subjects who are found to have de novo (i.e. not present at baseline) small pericardial effusions on study will be followed with weekly ECHOs and ECGs for the first month after the new pericardial effusions are first noted or until the effusion has regressed (if sooner). Treatment for the effusion may be administered at the discretion of the Investigator. Study drug will not be discontinued in these subjects, at the discretion of the investigator, unless the effusion progresses.

Subjects presenting with de novo (i.e. not present at baseline) minimal or trivial pericardial effusions visualized by ECHO will be permitted to stay on study treatment since these findings would be considered to represent physiological levels of fluid and typically represents a normal amount of pericardial fluid in a disease-free state. However, such subjects will have increased safety monitoring, including weekly ECHOs and ECGs for 2 weeks to validate the finding as non-pathologic or until the effusion has regressed (if sooner), followed by a return to the regular schedule.

In patients who develop a significant pericardial toxicity, blood will be collected and tested for antinuclear antibody (ANA) and anti-histone antibody testing.

In exceptional circumstances where ECHO is not considered a technically optimal assessment of pericardial space (e.g., overweight subject), other methods (e.g., MRI) should be used for pericardial assessments. In such cases, the guidelines provided in Table 9-4 would not apply, and the evaluation should be performed in consultation with the Medical Monitor. In the event that a pericardial effusion is first identified by a method other than ECHO, efforts should be made to obtain an ECHO for assessment of effusion size.

### 9.3.5. Management of chest pain

Subjects who report chest pain, even without other complaints suggestive of pericarditis, effusion, hemodynamic compromise, or tamponade, will require careful questioning to characterize this symptom. Pericarditis typically presents with dull or sharp precordial or substernal pain that may radiate to the neck, trapezius ridge (especially the left), or shoulders. This pain ranges from mild to severe. Unlike ischemic chest pain, pain due to pericarditis is usually aggravated by thoracic motion, cough, breathing, or swallowing food and may be relieved by sitting up and leaning forward. Tachypnea and nonproductive cough may be present. Fever, chills, and weakness are common.

If the subject's symptoms suggest pericarditis, history and physical exam including careful auscultation for pericardial friction rub and an ECG should be performed. In the first stages of pericarditis, pericardial effusion may or may not be found on ECHO. ECHO in a week or two may be more useful.

#### 9.4. Concomitant therapy

### 9.4.1. Permitted concomitant therapy

**Supportive care/Palliative care:** Supportive and palliative care for disease related symptoms may be administered at the investigator's discretion including the use of analgesics.

**Anti-emetics:** Subjects should be premedicated for nausea and vomiting as these have been associated with the administration of mocetinostat.

Transfusions: Subjects may receive transfusions as necessary.

### 9.4.2. Cautioned concomitant therapy

**CYP450 substrates:** In vitro human liver microsome assays demonstrated that mocetinostat had differing inhibitory effect on the metabolism of medications by cytochrome P450 CYP2C9 (strong inhibition for diclofenac but no inhibition for tolbutamide). In in vitro assays using specific chemical inhibitors and individual human recombinant CYP enzymes (cDNA expressed supersomes), mocetinostat was found to be metabolized mainly by CYP2E1 and to a lesser extent by CYP3A4 and CYP2C8. Caution should be used when mocetinostat is administered to Subjects taking medications metabolized by CYP2C9 or that inhibit or induce metabolism by CYP2E1. See Appendix A, Table 20-1 and Table 20-2, for examples of medications of interest. If a subject is taking a drug on one these lists, it is encouraged to substitute a different medication if possible.

**Gastric acid inducers:** Medications that directly increase gastric pH such as short-acting antacids should be avoided 4 hours before and 1 hour after administration of mocetinostat. Medications that affect gastric acid secretion, such as H2 antagonists or proton pump inhibitors will be allowed.

**QTc Prolongating medications:** Patients currently receiving treatment with risk of prolonging QTc or inducing torsade de pointes are recommended to either discontinue or switch to a different medication prior to study enrollment. Prohibited QTc prolonging medications are listed in Table 20.4. Concomitant use of potential QTc prolonging agents should be discussed with the sponsor and evaluated based on a case by case basis.

**Substrates and inhibitors of P-gp:** Mocetinostat was shown to be a substrate and an inhibitor of P-gp. Therefore, P-gp sensitive substrates and strong inhibitors of P-gp should be used with caution (Table 20.3).

**Anti-coagulation:** At the discretion of the investigator and under medical supervision, Subjects may continue to receive prophylactic dose levels of anti-coagulants (except warfarin and coumarin derivatives) and chronic supportive care agents (e.g. ESAs) established at least 4 weeks or more prior to first dose of study treatment and used in a consistent regimen unless reduced or discontinued. The investigator should take into consideration the use of anticoagulants in subjects at risk of bleeding due to low platelet count.

### 9.4.3. Prohibited concomitant therapy

**Other anticancer treatments:** Other anti-cancer treatment including chemotherapy and radiotherapy are prohibited during this study. If such agents are required, then the patient must be discontinued from the study.

**Growth factor support:** Prophylactic use of growth factor support to avoid anticipated study treatment side effects or as a substitute for a scheduled dose reduction. However they may be used in case of severe anemia (hemoglobin < 80 g/L or 8 g/dL) or neutropenia (< 1.0 x 109/L or 1000/ mm3) at discretion of the Investigator. Use of growth factors must be documented in CRDB.

**Warfarin or coumarin derivatives:** Therapeutic doses of warfarin or other coumadin derivatives anticoagulants are not permitted. Warfarin has a narrow therapeutic range and mocetinostat is possibly affected by CYP2C9, the main metabolizing enzyme of warfarin.

**Drugs with QTc prolonging activity**: As listed in Table 20.4. This list is not comprehensive and any questions should be reviewed with the pharmacist and discussed with the sponsor.

**CYP3A4 inhibitors and inducers:** As listed in Table 20.5. This list is not comprehensive and any questions should be reviewed with the pharmacist and discussed with the sponsor.

**Herbal medications/preparations**: Hernal medications and preparations are not allowed throughout the study, as a potential drug- drug interaction is always possible. These herbal medications include, but are not limited to: St. John's wort, Kava, ephedra (ma huang), gingko biloba, dehydroepiandrosterone (DHEA), yohimbe, saw palmetto, and ginseng. Patients should stop using these herbal medications at least 7 days prior to first dose of study treatment.

**Contraceptives:** Hormonal contraceptives may be affected by cytochrome P450 interactions, and are therefore not considered effective for this study, since induction of CYP3A4 may not be excluded in patients receiving mocetinostat.

**Gastric acid inducers:** Medications that directly increase gastric pH such as short-acting antacids should be avoided 4 hours before and 1 hour after administration of mocetinostat. Medications that affect gastric acid secretion, such as H2 antagonists or proton pump inhibitors will be allowed.

**Immunosuppressants:** Chronic administration of corticosteroids (>10 days), patients receiving increasing corticosteroids or another immunosuppressive agent will be prohibited. The following uses of corticosteroids are permitted: single dose, topical applications (e.g., rash), inhaled sprays (e.g., obstructive airways diseases), eye drops or local injections (e.g., intra-articular).

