#### 20.3. List of P-gp substrates to be used with caution

This list of P-gp substrates to be used with caution is not comprehensive and any questions should be reviewed with the pharmacist and discussed with the sponsor.

Table 20-3. List of P-gp substrates to be used with caution
P-gp substrates
Aliskiren
Ambrisentan
Colchicine
Dabigatran
Digoxin
Everolimus
Fexofenadine
Imatinib
Lapatinib
Maraviroc
Nilotinib

Posaconazole
Ranolazine
Saxagliptin
Sirolimus
Sitagliptin
Tolvaptan

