### 20.5. List of prohibited CYP3A inhibitors and inducers

This list of prohibited CYP3A inhibitors and inducers are not comprehensive and any questions should be reviewed with the pharmacist and discussed with the sponsor.

Table 20.5. List of prohibited CYP3A inhibitors and inducers						
Strong CYP3A inhibitors	Moderate CYP3A inhibitors	Strong CYP3A inducers	Moderate CYP3A inducers			
clarithromycin	amprenavir	carbamazepine *	bosentan			
conivaptan	aprepitant	fosphenytoin *	efavirenz			
grapefruit juice	diltiazem	nevirapine	etravirine			
indinavir	atazanavir	oxacarbazepine*	felbamate *			
itraconazole	cimetidine	phenobarbital *	modafenil			
ketoconazole	ciprofloxacin	phenytoin *	nafcillin			
lopinavir with ritonavir	darunavir with ritonavir	primidone *	pioglitazone			
nefazodone	elvitegravir	rifabutin	rufinamide *			
nelfinavir	erythromycin	rifampin	talviraline			
posaconazole	fluconazole #	ritonavir	tipranavir			
saquinavir	schisandra sphenanthera	St. John's Wort	topiramate * (>200 mg/day)			
star fruit juice	tipranavir with ritonavir					
telithromycin	verapamil					
voriconazole						

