# flucenezale inhibition is done dependent and use may be considered on a case by case basis						

# fluconazole inhibition is dose-dependent and use may be considered on a case by case basis

\* These drugs are Enzyme Inducing Anti-Epileptic drugs of Medicine's "Clinically Relevant" Table; and from [50].

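### Sections 9.4.2 and 9.4.3 allow H2 antagonists without exception while Table 20.5 prohibits cimetidine, and no sentence says that a prohibition overrides a caution or permission

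*Combined protocol and SAP*

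**What the plan says.** **Permission.** Section 9.4.3 of the protocol, although headed as prohibited therapy, closes its gastric acid paragraph with "Medications that affect gastric acid secretion, such as H2 antagonists or proton pump inhibitors will be allowed". Section 9.4.2 carries the same sentence. Neither names an exception.

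**Prohibition.** The CYP3A4 paragraph of Section 9.4.3 defines the barred inhibitors and inducers by reference: "As listed in Table 20.5". Table 20.5 names cimetidine (moderate inhibitor), "posaconazole" (strong inhibitor) and phenytoin (strong inducer). The one exception written into the table is a footnote: "fluconazole inhibition is dose-dependent and use may be considered on a case by case basis".

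**Caution lists.** Table 20-3 (P-gp substrates to be used with care) also lists "Posaconazole". Table 20-1 (drugs metabolized by CYP2C9) also lists phenytoin. For Tables 20-1 and 20-2, Section 9.4.2 goes no further than "If a subject is taking a drug on one these lists, it is encouraged to substitute a different medication if possible".

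**Consequence.** Section 13.1 puts prohibited drug use among the criteria that require study treatment to end early.

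**The concern.** Two members of staff who each follow the text literally can reach opposite decisions. One reads that H2 antagonists are allowed and lets a patient take cimetidine alongside mocetinostat. The other finds cimetidine in Table 20.5 and refuses it or, if it has already been taken, applies Section 13.1 and stops mocetinostat. Whether a relapsed or refractory patient stays on treatment could then depend on which paragraph was read.

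Posaconazole and phenytoin raise a weaker form of the question. A reader who looks only at the caution table sees a drug that may be used with care. A reader who looks at Table 20.5 sees a ban.

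**Working it through.** The plan gives no figure to reproduce, so the check is a comparison of the entries.

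**Step 1. Status of each drug.**

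| Drug | Permission or caution | Prohibition | Can both be obeyed? |
|---|---|---|---|
| Cimetidine | Allowed by class, Sections 9.4.2 and 9.4.3 | Table 20.5, moderate inhibitor | Not as written: the class is allowed with no exception |
| Posaconazole | Caution, Table 20-3 | Table 20.5, strong inhibitor | Yes, by not using it |
| Phenytoin | Caution, Table 20-1 | Table 20.5, strong inducer | Yes, by not using it |

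The only step from outside the documents is that cimetidine is an H2 antagonist. That is ordinary drug-class knowledge.

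**Step 2. How many entries are involved.** Table 20.5 has 14 strong inhibitors, 13 moderate inhibitors, 11 strong inducers and 11 moderate inducers: 14 + 13 + 11 + 11 = 49. One of these, cimetidine, also falls under the permission sentence. The caution tables hold 16 (Table 20-1), 3 (Table 20-2) and 17 (Table 20-3) drugs: 16 + 3 + 17 = 36. Matched by name, two of the 36 recur in Table 20.5 (phenytoin and posaconazole) and none in Table 20-4.

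**Step 3. Is there a rule that settles it?**
- The CYP3A criterion in Section 6.3 excludes patients whose moderate or strong inhibitor or inducer cannot be stopped or switched, and requires strong ones to be stopped before treatment. It governs entry, not a drug begun later. It also refers to Tables 20-1 to 20-5 together, without ranking caution against prohibition.
- Section 9.4.3 and the note above Table 20.5 send questions to the pharmacist and sponsor. That helps only a reader who sees that there is a question.
- Table 10-1 schedules medication review at every listed visit. Review detects use but does not say which entry governs.
- No sentence in Section 9.4 or Appendix A gives precedence.

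**Step 4. Which entry to keep.** Where the authors wanted leeway within Table 20.5 they wrote it down, for fluconazole. They wrote none for these three drugs, so the prohibition is the natural reading.

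**The case against.** The best defence is that the H2 sentence is about gastric pH. It follows the timing rule for short-acting antacids and can be read as saying only that drugs acting on acid secretion need no such spacing. Table 20.5 bars named drugs on a different ground, CYP3A, and a ban by name normally outranks a general class permission. This reading is plausible and probably what was meant, but the protocol does not state it. A reader told without qualification that the class is allowed has no reason to consult another table.

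It is also fair that staff who see the prohibition would usually choose another H2 antagonist or a proton pump inhibitor, so Section 13.1 would seldom be reached. That stands, and it keeps the point minor.

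A reader might go further in four directions that the documents do not support.
- **Posaconazole and phenytoin as contradictions.** The tables are organized by mechanism, one drug can properly appear in two, and obeying the ban satisfies the caution.
- **A caution appendix at odds with the bans throughout.** Warfarin appears in Table 20-1, but Sections 6.3, 9.4.2 and 9.4.3 bar it consistently. Section 9.4.2, for example, continues "prophylactic dose levels of anti-coagulants (except warfarin and coumarin derivatives". The anticancer and immunosuppressive drugs in the caution tables meet a ban only through class assignments that those tables do not make.
- **The anti-emetic instruction in Section 9.4.1 as a second conflict.** Table 20.5 lists aprepitant, an anti-emetic by ordinary drug class. Other anti-emetics satisfy both rules, so only a cross-reference is missing.
- **A known change in mocetinostat exposure.** The documents disagree on the pathway. Section 9.4.2 says the drug is metabolized mainly by CYP2E1 and "to a lesser extent by CYP3A4 and CYP2C8". The nonclinical metabolism text in Section 3.2.7 names CYP3A4 first and CYP2E1 only as possible. No exposure effect can be sized in either direction.

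**Conclusion.** The point holds as a minor conduct and safety inconsistency. For a drug started on study, cimetidine is both allowed and prohibited. For posaconazole and phenytoin, a caution and a prohibition stand side by side with no stated order.

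The conclusion assumes that cimetidine falls within the H2 class named in the permission, and that the authors meant Table 20.5 to hold except where footnoted.

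The number of patients affected cannot be estimated, because the documents give no frequency of use for these drugs. If none is prescribed on study, nothing changes.

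A reader might infer a threat to the primary result, since a patient could be taken off drug. The documents do not support that. The Section 14 decision rules do not depend on the concomitant drug lists. Under Section 13.2.2, a patient who stops for this reason continues radiological assessment, subject to that section's usual end points. No effect on type I error, power or sample size follows.

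**What to change.** 1. In the gastric acid paragraph of both Section 9.4.2 and Section 9.4.3, write: 'H2 antagonists (except cimetidine, see Table 20.5)'. This edit is needed in its own right, because the permission also sits inside Section 9.4.3, where the sentence in item 2 would not reach it.
2. Open Section 9.4 with: 'If a drug permitted in Section 9.4.1 or cautioned in Section 9.4.2 is also prohibited in Section 9.4.3, Table 20-4 or Table 20.5, the prohibition applies.' This settles posaconazole and phenytoin and supplies the missing link for aprepitant.
3. Keep the fluconazole footnote as written. Leave Tables 20-1 to 20-3 unchanged: their entries describe metabolic and transport pathways, and deleting any would add nothing once item 2 is in place.

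The cost is two edited sentences and one new one. Design, sample size, data collection and analysis stay as they are. On the reading that Table 20.5 governs, no prohibition is added or lifted.

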# **10.0 EVALUATION DURING TREATMENT/INTERVENTION**

### 10.1. Evaluation Summary Chart.

Table 10-1 lists all of the assessments and indicates with an "X", the visits when they are performed. All data obtained from these assessments must be supported in the patient's source documentation. All visits can take place 3 days before or 3 days after the specified study visit (total window of 7 days) except for the time window for the end of treatment and safety follow-up visit which is +7 days.

Table 10-1. Study flow	i and evaluatior	ו						
			Evalua	tion Summa	ary			
Day of Cycle	Cycle 1 Day 1 (- 3 days)	Cycle 1 Day 8 (+/- 1 day)	Cycle 1 Day 15 (+/- 1 day)	Cycle 1 Day 22 (+/- 1 day)	Cycle 2 Day 1 (+/- 3 days)	Cycle 2 Day 15 (+/- 1 day)	Cycle 3 Day 1 + onward (+/- 3 days)	End of Study
	1		 	reatment				1
Mocetinostat		Con	tinuous dosii	ng, three day	/s per week by	mouth	×	×
Pill Diary Review			Histo	rv+ Physica			 	^
Toxicity Assessment a,	x			Continu	ous Assessme	nt		x
Medication review	X	X	X	Х	Х	Х	Х	X
Physical exam	X	Х	Х	Х	Х	Х	Х	X
ECOG	X		X		X		X	X
Vital signs b	X		Х		Х		Х	x
Ŭ	•	1	Laborato	ry assessm	ents	1	1	1
Hematology c	X (- 7 days)		x		x	x	x	x
Chemistry c	X(-7 days)		Х		Х	Х	Х	X
DLBCL arm only: Chemistry specific to tumor lysis syndrome d		X( day 2,	3, 4 of cycle	e 1 only)				
Coagulation (PT/PTT)	X (-7 days)			As clir	nically indicated			x
Pregnancy test (serum); for WOCBP only	X (-7 days)				x		x	x
,	•	1	Tumor	assessmen	nts		1	1
Radiographic assessment e	X (-28 days)						X Q 8 wks for 0-6 mo; Q 12 wk for 6-12 mo; Q16 wk after 1 yr	X Q 8 wks for 0-6 mo; Q 12 wk for 6-12 mo; Q16 wk after 1 yr
Bone Marrow biopsy	As clinically indicated		** At time	e of complete	e response if BN	/l involved pr	ior	
			Safety	assessmen	nts			
ECG	X (-28 days)		x		X (predose)	x	As clinically indicated	x
Cardiac imaging (ECHO)	X (-28 days)		x		X (predose)	x	As clinically indicated	x
			Bi	omarkers				_
CREBBP/EP300 screening	Pre- screening							
Collection of fresh tumor from biopsy/resection			X (option al)				X (optional)	X (optional at relapse)

Research blood sample	X (-7 days)	Х	Х		

a. Assessed including type, severity, timing and relationship to study drug using NCI common Toicity Criteria version 4.0

- b. Weight, blood pressure, pulse
- c. CBC with differential, Chemistry (Potassium, sodium, calcium, magnesium, chloride, inorganic phosphorus, ALT/SGPT, AST/SGOT, alkaline phosphatase, total bilirubin, direct bilirubin, LDH, Gamma GT, Serum creatinine, urea or blood urea nitrogen (BUN), lipase, albumin, uric acid)
- d. Uric acid, potassium, sodium, calcium, inorganic phosphorus and serum creatinine
- e. CT scan with contrast, unless contraindicated, of the chest, abdomen, and pelvis, neck; PET scan for patients with DLBCL (combination PET/CT may be used); MRI may be substituted for CT scan if patients are intolerant of CT scans with contrast

